	To determine whether PF-04457845 QD weeks is superior to placebo in improving participant-reported quality of life.	Quality of Life Enjoyment and Satisfaction Questionnaire-18 item version (Q-LES-Q-18)	Δ in total and subscale scores	
	To determine whether PF-04457845 QD is superior to placebo in reducing cannabis craving.	Marijuana Craving Questionnaire	Δ in total score	

APPROVED BY THE YALE UNIVERSITY IRB 5/1/2022

	To determine whether PF-04457845 QD is superior to placebo in reducing cognitive deficits.	Cogstate Battery	Δ in composite score	
	To determine whether PF-04457845 is superior to placebo in reducing sleep disturbances.	Sleep report questionnaires	Δ in total score	
		Visual confirmation (by video)	% of confirmed observations	Over 8 weeks
	To assess adherence to PF-04457845.	PF-04457845 plasma concentrations	Difference in PF-04457845 plasma concentrations between placebo and PF- 04457845 groups	Over the time period starting the first dose until the last dose
		Anandamide plasma concentrations	Difference in plasma anandamide concentrations between placebo and PF- 04457845 groups	first dose until the last dose

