6.4.1 Male Participants: From signing of informed consent until 2 weeks after the last dose of study medication, non-sterilized male participants who are sexually active with a female partner of childbearing potential must agree to use barrier contraception (e.g. a condom with or without spermicidal cream or jelly). In addition, they must be advised not to donate sperm during this period.

6.4.2 Female Participants: From signing of informed consent until 2 weeks after the last dose of study medication, female participants of childbearing potential (Women of Child Bearing Potential: WOCBP) who are sexually active with a non-sterilized male partner must use a highly effective method of contraception (from the list below). In addition, they must be advised not to donate ova during this period.

6.4.3 Methods of Contraception: Acceptable contraceptive methods for WOCBP participants include: double barrier contraception or a combination of a barrier contraception and a hormonal implant, injectable, combined oral contraceptive, or a male partner who has had a vasectomy; IUD or tubal ligation.

6.5 **Pregnancy:** If any participant is found to be pregnant during the study, participation in the treatment phase must be immediately terminated. The participant should stop taking the study medication and return any remaining study medication as soon as possible. If possible, the participant should complete the follow up phase which is to collect safety data. Furthermore, the investigator should make every effort to ensure that the participant has established follow up care with a medical provider (OBGYN). The pregnancy should be followed up by the site investigator to determine outcome (including spontaneous or voluntary termination), details of birth, and the presence or absence of any birth defects, congenital abnormalities, or maternal and/or newborn complications.

6.6 Randomization Criteria: Participants who meet all inclusion and exclusion criteria will be randomized at the time of the Week 1 visit in a 1:1 ratio of PF-04457845 to placebo using random block sizes of 2 and 4, stratified by site and degree of cannabis use (CUD at the level of moderate (4-7 [of 11] symptoms) or severe (8-11 [of 11] symptoms)) based on DSM-5 criteria. These variables were chosen because they are the most likely to strongly affect outcomes measures. Random treatment assignment will be done using a centralized randomization process.

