7.0 STUDY INTERVENTION

7.1 Allocation to Treatment: Participants will be assigned a unique subject ID number that will be recorded in the randomization log. Then, prior to dosing, a randomization number will be allocated. This number will be retained throughout the study and will correspond to a treatment schedule determined by a randomization code. Participants will be made aware that there is a 50% chance that they will receive a placebo as a part of this research protocol.

All randomizations will be maintained centrally by the Coordinating Center, using the REDCap application. Participants will be randomized in a 1:1 manner. The randomizations will be stratified by site and severity of cannabis use (CUD at the level of moderate (4-7 [of 11] symptoms) or severe (8-11 [of 11] symptoms)) based on DSM-5 criteria.

7.2 Breaking the Blind: All study personnel will be blinded to the study treatment. To minimize the potential for bias, treatment randomization information will be kept confidential and will not be released to the investigator or investigator site personnel until after the study database has been locked.

At the initiation of the study, the study site will be instructed on the method for breaking the blind. Blinding codes will only be broken in emergency situations for reasons of participant safety, where knowledge of treatment allocation *is necessary* to provide emergency care. Whenever possible, the investigator or co-investigator should consult with a member of the Coordinating Center prior to breaking the blind. When the blinding code is broken, the date, time, and reason the blind is broken must be fully documented in the source documents.

To preserve the blind, blood will be sampled for PF-04457845 assay from all participants regardless of whether they have been randomized to PF-04457845 or placebo.

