Participants will be provided with a cellphone that has the hardware, software, and service necessary to transmit high quality video. Prior to randomization, each participant will receive training on how to use the cell phones and also trained on the CAROMA compliance protocol. For this, each participant will be placed in one clinic office with the phone. A research staff member will video call the participant from another location in the clinic and will observe the participant consuming one M&M candy (or similar) with a glass of water. All participants will need to have at least one successful training session prior to randomization.

The CAROMA video calls will not be recorded. Immediately following each call, research staff will document visual confirmation of the participant taking his/her study medication, the time that the medication was taken.

7.6.2 *Plasma PF-04457845 Levels*: Adherence will also be confirmed later by measuring PF-04457845 levels in plasma from blood sampled at Week 1, Week 5, and Week 9 study visits.

7.6.3 Plasma Anandamide Levels: Adherence will also be confirmed later by measuring anandamide levels in plasma from blood sampled at Week 1, Week 5, and Week 9 study visits.

7.6.4 Weekly Pill Counts: At each in-person visit (Week 3, Week 5, Week 7, and Week 9), research staff will reconcile the number of capsules actually returned with the number that were expected to be returned. Virtual pill counts will also be conducted via video call at each remote study visit (Week 2, Week 4, Week 6, and Week 8) to reconcile the number of remaining capsules the participant has in their possession with the expected number of remaining capsules.

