10.3.1 PF-04457845 Levels: Blood will be sampled for PF-04457845 levels as specified in the Schedule of Procedures (1.5 Schedule of Procedures: Table 2). Given that adherence will be confirmed visually, the PF-04457845 levels will be assayed in only a random sampling of approximately 1/3 of participants from each site to confirm adherence, as specified by the Coordinating Center. Assays will be conducted by laboratory of [name] at Northeastern University using a proprietary assay with existing permission from SpringWorks and Jazz Pharmaceuticals. The serum sample to be analyzed for PF-04457845 levels should be collected in one 4 cc lavender top tube (tube containing K2-EDTA). Blood samples should be collected as close to approximately 1 hour after the participant has taken their daily dose of study medication (PF-04457845/placebo). The time at which the blood sample has been drawn at should be documented, along with the time that the study medication was taken that day. The sample should then be centrifuged at approximately 1700g for about 10 minutes at 4 degrees Celsius, pipetted into appropriately labeled 1.5 mL screw capped polypropylene tubes (1 mL of serum sample per tube; 2 polypropylene tubes), and then stored in a -80 degree Celsius freezer within 1 hour of collection. Samples will be stored on site until they are to be sent directly to WuXi by each site, at the end of the study.

Shipment of Pharmacokinetic Samples: Each site will store blood samples to be assayed for PF-04457845 levels on site in a -80 degree Celsius freezer. Samples will be stored on site, and will be shipped on dry ice directly to the lab of [name] at Northeastern University, in batches of at least 50 samples. The Coordinating Center will instruct each individual site on which random sampling of participants should be shipped.

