14.2.2 Secondary Outcomes: The same analytic strategy will be followed for secondary outcomes compared to the primary outcome. Primary analyses will be based on ANCOVA with multiple imputation on the modified intent-to-treat sample, secondary analyses will include mixed models, tipping point analyses and analyses of the per protocol sample. The emphasis will be on effect estimation. Testing in the primary analyses will be adjusted using the Bonferroni-Holm method. For each eCB, plasma levels will be assessed by fitting a mixed effects model with treatment, time, site, and the interaction terms as fixed effects, and tobacco use as covariate. Exploratory analyses will be conducted to assess the effect of variables such as gender and use of other substances on endocannabinoids. Since we expect floor effects for the blood levels of PF-04457845 in the placebo condition, PF-04457845 blood level will be assessed by using non-parametric models (226, 227) with treatment, time, site, and the interaction terms as factors.

14.3 Safety Analysis: The review and summary of safety will be performed on the modified intent-to-treat sample. Events or abnormalities will be searched from the time of the first dose until 5 half-lives after the last dose. Clinical laboratory data will be summarized quantitatively using descriptive statistics such as changes from baseline summarized by mean, standard deviation, median, minimum and maximum, and summarized qualitatively by tabulating clinical abnormalities. Vital signs, BMI, weight will be summarized using descriptive statistics. Group differences in the percentage of participants who report AEs or exhibit clinically significant changes during 1) 8-week treatment phase (from the first dose until the last dose), and 2) the 4-week follow up phase (to assess any lingering post treatment safety issues) will be summarized in tabular form and presented. Data permitting, exploratory analyses may be performed to evaluate the statistical significance of between-group differences (e.g. using Fisher's exact tests for adverse events, t-tests or non-parametric equivalent for changes in continuous measures) and evaluation of the effects of duration of drug exposure or drug dose on any adverse events (e.g. using exact logistic regression) and laboratory measures (e.g. using mixed effects models).

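### The drug-level adherence endpoint is an active-versus-placebo difference, so it does not estimate what fraction of active participants took the drug, and about half of its assays are expected to fall on placebo.

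*Combined protocol and SAP*

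**What the plan says.** Under the exploratory objective of assessing adherence, Table 10 lists three measures: the percentage of video observations confirmed, the "Difference in PF-04457845 plasma concentrations between placebo and" active groups, and the corresponding difference for anandamide. Section 4.2.3 item 5b lists plasma concentrations without saying how they will be summarised.

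Section 7.2 has everyone bled to protect the blind: "blood will be sampled for PF-04457845 assay from all participants". Section 7.6.2 says adherence will also be confirmed by "measuring PF-04457845 levels in plasma from blood sampled at Week 1, Week 5, and Week 9 study visits". Section 10.3.1 limits the assays: "the PF-04457845 levels will be assayed in only a random sampling of approximately 1/3 of participants from each site to confirm adherence". It does not restrict the draw to the active arm, and section 6.6 has participants "randomized at the time of the Week 1 visit in a 1:1 ratio of PF-04457845 to placebo". On timing, 10.3.1 says "Blood samples should be collected as close to approximately 1 hour after the participant has taken their daily dose of study medication".

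Section 14.2.2 expects floor effects on placebo, so "PF-04457845 blood level will be assessed by using non-parametric models" with treatment, time, site and their interactions as factors. I found no concentration threshold, no percentage-with-drug summary and no rule for what confirms adherence.

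**The concern.** Placebo participants are not given PF-04457845, and section 3.4.1 reports that it could not be detected in the placebo group of the preliminary study. A comparison with a group sitting at the assay floor therefore tests whether anyone in the active arm took the drug. Adherence is a different quantity: the fraction who took it.

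Section 3.4.2 shows how such a contrast may be read. There, drug and anandamide levels that were higher on active than on placebo were taken as confirming adherence. If the same reading is applied here, a clear between-arm difference could be offered as biological support for adherence when most active participants had no drug on board. That would matter most when explaining a null efficacy result.

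Two further features weaken the measure. Placebo assays beyond a few controls add almost nothing about adherence. And a sample drawn about an hour after a dose mainly shows that day's dose, not the preceding days.

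**Working it through.** **1. The plan's own figures.** No sample size, threshold or power is given for this endpoint. Section 14.1 sizes the primary endpoint: 2 × (1.960 + 0.842)² / 0.42² = 89 per arm, 178 in total, which reproduces. 178 / 0.75 = 237.3, against 237 stated. These serve below only as alternative bases for the number assayed.

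**2. Number of assays.** 260 / 3 ≈ 87, so about 43 per arm at 1:1. If the draw ignores arm, the active count has a 95% range of 36 to 51. On 237 participants: 79 assays, about 40 per arm. On 178 completers: 59 assays, about 30 per arm.

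**3. Smallest significant result.** Assume placebo samples and active non-takers are all undetectable, one time point, two-sided 0.05, 43 per arm.
- Fisher exact, 5/43 vs 0/43: p = 0.055. 6/43 vs 0/43: p = 0.026. So 6 of 43 (14%) is enough.
- Tie-corrected rank-sum, closer to the planned analysis: 4/43 vs 0/43 gives p = 0.042. So 4 of 43 (9%) is enough.

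**4. True share of takers giving an 80% chance of significance.** Solve P(X ≥ c) = 0.80 for X ~ Binomial(n, π), where c is the smallest significant count. At each n shown, c is 6 for Fisher and 4 for rank-sum.

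| Basis | Active assays n | Fisher (c = 6) | Rank-sum (c = 4) |
|---|---|---|---|
| 260 | 43 | 17.8% (1 in 5.6) | 12.5% (1 in 8) |
| 237 | 40 | 19.0% (1 in 5.3) | 13.4% (1 in 7.5) |
| 178 | 30 | 25.1% (1 in 4) | 17.6% (1 in 5.7) |

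**5. What a proportion would show.** With 43 active assays and exact (Clopper-Pearson) 95% intervals, 41/43 = 95% (84–99%) and 7/43 = 16% (7–31%). The intervals are far apart, although a between-arm test would be significant for both.

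**6. Timing.** Section 3.2.1 gives a mean time to peak of 2 h, multi-phasic elimination with half-life 12–23 h, and 2–3-fold accumulation. As an assumption, take one compartment with first-order absorption and C(t) ∝ e^(−kt) − e^(−ka·t), with ka set for a 2 h peak. Accumulation R = 1 / (1 − 2^(−24/t½)), so R = 2 needs t½ = 24 h and R = 3 needs about 41 h. For someone who missed the three previous doses but took the visit-day dose, the 1 h level relative to full adherence is [C(1) + Σ C(1+24j), j ≥ 4] / [Σ C(1+24j), j ≥ 0]. This is 54% for R = 2 and 52% for R = 3. A 12 h half-life would give 72%, but it implies only 1.33-fold accumulation, so I do not rely on it.

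**7. Which visits the timing point reaches.** Week 1 is the randomisation and first-dose visit, so its sample cannot show sustained adherence. Week 9 is day 57, after the 8-week treatment phase, and Table 1 shows no study drug there. The 1-hour rule then has no scheduled dose to refer to. Week 5 is the one sample to which the criticism clearly applies.

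**The case against.** The strongest reply is that the plan never says a significant difference confirms adherence. Section 14.2.2 puts the emphasis on effect estimation, and the size of the difference does carry information. At 6 of 43 takers, the probability that an active value exceeds a placebo value (ties counted half) is 0.5 + 0.5 × 6/43 = 0.57, against 1.0 with full adherence. Section 14.0 also tabulates compliance by group and time, with descriptive statistics, so a largely undetectable active arm would probably be seen.

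Plasma level is also only a cross-check. Section 10.3.1 limits assays to a third because adherence is confirmed visually. Section 7.6.1 has swallowing observed by video Monday to Friday and treats a missed call as non-adherence, and section 7.6.4 adds pill counts.

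Much of this stands, and it rules out several stronger readings that a reader might infer:
- **That the trial would declare adherence confirmed with about 1 in 6 taking the drug.** This needs a p < 0.05 rule that the documents do not contain, and it needs video and pill counts to miss the problem as well.
- **That the anandamide measure has the same flaw.** Anandamide is endogenous. Placebo means in Table 5 run from 0.270 to 0.476 ng/ml, and section 10.3.2 does not limit those assays to a third of participants.
- **That the 1-hour rule undermines every sample.** It clearly bears only on Week 5, and 10.3.1 already requires draw time and that day's dose time to be recorded.

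What the reply does not answer is that the named endpoint is the wrong summary. A concentration difference mixes the share who took the drug with the level among those who did, and roughly half the assays go to an arm where the answer is known in advance.

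**Conclusion.** The concern holds for PF-04457845 concentration. As defined, the endpoint does not estimate the fraction of active participants who took the drug. It can be significant with 6 of 43 active samples positive, and it has an 80% chance of significance when the true share of takers is between about 1 in 4 and 1 in 8.

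Those figures assume undetectable levels in placebo participants and non-takers, one time point, and significance at two-sided 0.05 as the yardstick. That yardstick is mine, not the plan's. The even split of assays is an expectation under random sampling, not a quota. The 52–54% timing figure rests on an assumed one-compartment model matched to the stated accumulation.

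The effect is confined to the biological cross-check on an exploratory adherence objective. The primary efficacy test and the per-participant adherence measures are untouched. The change is worth making because it costs almost nothing.

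**What to change.** **Table 10.** Replace the between-group difference for PF-04457845 with the percentage, and exact 95% interval, of assayed active-arm participants with quantifiable drug, or with drug above a level stated in advance, at each on-treatment sample. Align section 14.2.2. The documents give no assay limit or threshold, so the sponsor must supply one before unblinding.

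**Section 10.3.1.** Keep bleeding everyone. Have an unblinded party outside the sites select the samples so that most of the same number of assays come from the active arm, plus a few placebo controls. For illustration, 80 active and 7 placebo assays use the same 87, and 76/80 would give 95% (88–99%). Sites should not be able to infer allocation from which tubes are requested, so stored tubes beyond the selected ones should be shipped, with results withheld until database lock.

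**Timing.** State that the Week 5 level largely reflects that day's dose and is weak evidence about earlier days. Reconcile the 1-hour rule in 10.3.1 with the Week 1 first-dose visit and the Week 9 visit on day 57. I do not propose a different draw time, because that could alter when the capsule is taken (section 7.4).

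**Cost.** Wording changes, one unblinded list and shipment of more stored tubes. No extra assays or blood.

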5.0 STUDY DESIGN AND DESCRIPTION

5.1 Study Design: The efficacy, safety and tolerability of the Fatty Acid Amide Hydrolase (FAAH) Inhibitor PF-04457845 in adults with DSM-5 current Cannabis Use Disorder (CUD) will be evaluated in a 4-site (Columbia University, Johns Hopkins, Medical University of South Carolina and Yale University), randomized, double-blind, placebo-controlled, parallel-group, outpatient clinical trial comparing PF-04457845 (4mg) and placebo DSM-5 CUD individuals (**Table 1**). Participants will be randomized in a 1:1 ratio to either PF-04457845 or placebo using a random block sizes of 2 and 4, stratified by site and degree of cannabis use (CUD at the level of moderate (4-7 [of 11] symptoms) or severe (8-11 [of 11] symptoms)) based on DSM5 criteria. These variables were chosen because they are the most likely to strongly affect outcomes measures. The trial includes a 1) 2-week screening phase, 2) 8-week treatment phase (for safety especially because the effects of the drug take ~ 2 weeks to washout). The duration of the treatment phase was chosen because the available toxicity data that Pfizer has collected is up to 12 weeks in humans.

During the screening period, participants will be required to set a quit attempt date that falls within the first week of treatment after at least 2 days of taking study medication. Participants will receive motivational interviewing to facilitate a quit attempt and will be rewarded for a successful attempt.

5.2 Study Population: Approximately 260 total participants (target of approximately 65 participants at each of the four participating sites based on competitive enrollment) of both genders and all ethnic/racial and socioeconomic backgrounds will be randomized for a total of 178 participants completing the study (approximately 45 subjects per site). All patients will meet DSM-5 criteria for cannabis use disorder. The complete inclusion and exclusion criteria is further described in Section 6.1 and Section 6.2. Final determination for eligibility will be made by each site's principal investigator.

5.3 **Duration:** Screening activities will be completed up to approximately 14 days (up to a maximum of 60 days) prior to randomization on the Week 1 visit. The total duration of this study (from signed consent to the last follow-up visit) will be approximately 14 weeks. The study is expected to last 3 years.

5.4 End of Study Definition: A participant is considered to have completed the study if he or she has completed the 8-week treatment phase of the trial.

6.0 STUDY POPULATION

6.1 Inclusion Criteria: Participants must meet all of the following inclusion criteria to be eligible for enrollment into the study:

- 1) Ages 18-60 years, inclusive (age verified using one form of picture identification with date of birth).
- 2) Male or Female.
- Individuals with DSM-V criteria for CUD of at least moderate severity (≥ 4 [of 11] symptoms).
- 4) Current cannabis consumption greater than or equal to 30 joints/month (approximately daily) over the past 3 months
- Positive for urinary THC-COOH on two separate occasions during screening (> 50ng/ml).
- 6) Primary drug currently being used is cannabis.
- 7) Primary method of cannabis consumption (>80% of the time) is smoking cannabis.
- Must express a willingness at screening to set a date within the first week of randomization to attempt to quit using cannabis.
- 9) Physically healthy i.e., no clinically unstable medical conditions at the discretion of the investigator.
- 10) Have given informed consent, and have capacity to consent and comply with study procedures.
- 11) Must be able to read English as per the judgment of the site investigators. Participants are required to be able to read because there are several self-administered measures that they must read, understand and provide written answers.
- 12) Must provide the name of at least 1 contact (preferably 2), who would assist study staff in locating them during the study period.
- 13) For women of childbearing potential (WOCBP) and men, willingness to practice birth control and to inform study staff immediately if either they (for women) or their partner (for men) becomes pregnant.
- 14) Must be willing to complete a number of study assessments and procedures remotely.

6.2 Exclusion Criteria: Participants presenting with any of the following exclusion criteria will be excluded from participation:

- Clinically significant unstable medical disorders (as determined by the site investigator) that will increase potential risk or interfere with study participation e.g., ongoing seizure disorder, uncompensated congestive heart failure, uncontrolled severe diabetes, uncontrolled severe hypertension, etc.
- 2) Laboratory tests with clinically significant abnormalities (as determined by the site investigator)
- 3) Positive urine toxicology screen for another drug with clinical evidence of use disorder for that drug (with the exception of THC-COOH at screening).
- 4) Pregnancy by history and or laboratory confirmation (serum HCG).
- 5) Lactation.
- 6) Other DSM-5 substance use disorder in the past three months (excluding cannabis, nicotine, caffeine, and mild alcohol use disorder [≤ 3 criteria]).
- 7) Physiological dependence on another prescribed (e.g. benzodiazepine), not prescribed licit (e.g. alcohol or benzodiazepine) or illicit substance (e.g. opioid) requiring medical management, such as alcohol, opioids, or benzodiazepines, excluding caffeine, and nicotine.
- 8) Abstinence from cannabis for more than 1 week at the time of randomization.

- Meeting DSM-5 criteria for current serious mental illness (e.g., major depression, bipolar disorder, schizophrenia, any psychotic illness, including substance-induced psychosis, and current substance-induced mood disorder.)
 - a. Individuals who meet criteria for current major depression at a mild severity* may be included at the discretion of the site principal investigator.
 * Per the DSM-5, current major depression at a mild severity is defined as: "Few, if any, symptoms in excess of those required to make the diagnosis are present, the intensity of the symptoms is distressing but manageable, and the symptoms result in minor impairment in social or occupational functioning."(228)
- 10) Lifetime history of DSM-5 bipolar disorder or any psychotic disorder.
- 11) Meeting DSM-5 criteria for any psychiatric disorder that may, according to t he investigator's judgment, require initiation of a pharmacological or non-pharmacological intervention over the course of the study.
- 12) Taking psychotropic medication/s that could interfere with interpretation of the study results or interact with study medication. Includes but is not limited to opioid analgesics, sedative hypnotics, or other known CNS depressants, etc. Exceptions include preexisting treatment with sleep agents, antidepressants for preexisting stable insomnia or depression, respectively.
- 13) Current moderate risk for suicide as measured by the Columbia Suicide Severity Rating Scale (CSSRS) suicidal ideation (in the last month) score of greater than 2 and a history of recent (past 1 year) serious suicide attempt (lethality score of >2 on CSSRS).
- 14) Current or past history of significant violence (past 2 years).
- 15) Currently in a residential treatment setting in which substance use is monitored and restricted, since the restricted access to drugs could represent an important confounding variable.
- 16) Participants who, in the investigator's opinion, would be unable to comply with study procedures or assessments, or would be unacceptable study candidates (e.g., poses threat to staff).
- 17) Participation in a clinical trial and receipt of investigational drug(s) during past 30 days.
- 18) Known allergy to FAAH-inhibitors.
- 19) Primary method of cannabis consumption (>80% of the time) is using vaporized cannabis or ingesting edibles.
- 20) Co-medication with CYP3A inhibitor, CYP3A inducers, or P-glycoprotein substrates, within 48 hours or 5 half-lives prior to baseline, at the discretion of the site investigator.

6.3 Concomitant Interventions: Participants must be instructed to not take any medications, including over-the counter products, vitamins, or supplements during the study without first consulting with and getting the approval of the investigator.

Similarly, since specific behavioral treatments developed for cannabis dependence e.g., MET or CBT may increase abstinence (17, 123), and in doing so obscure the effects of a medication treatment, participants will be asked to refrain from starting any such treatment until after completing the trial. Participants always have the option of dropping out from the trial to purse these or other interventions.

6.3.1 Pharmacokinetic interactions with PF-04457845: In vitro studies using recombinant human cytochrome P450 (CYPs) enzymes suggest that CYP3A4 is the predominant isoform responsible for the oxidative metabolism of PF-04457845. Therefore, drugs that induce or inhibit CYP3A4 may reduce or increase PF-04457845 levels. While not absolutely contraindicated, treatment with the following drugs should be carefully evaluated. The following list provides some, but not all, of the drugs knows to induce or inhibit CYP3A4:

- Drugs that Induce CYP3A4 reduce PF-04457845 levels which may result in sub-therapeutic levels of PF-04457845. This includes: Carbamazepine, Dexamethasone, Ethosuximide, Glucocorticoids, Griseofulvin, Phenytoin, Primidone, Progesterone, Rifabutin, Rifampin, Nafcillin, Nelfinavir, Nevirapine, Oxcarbazepine, Phenobarbital, Phenylbutazone, Rofecoxib, St. John's Wart, Sulfadimidine, Sulfinpyrazone, and Troglitazone.
- Drugs that Inhibit CYP3A4 increase PF-04457845 levels which may result in above normal levels of PF-04457845. This includes: Amiodarone, Anastrozole, Azithromzcin, Cimetidine, Clarithromycin, Clotrimazole, Cyclosporine, Danazol, Delavirdine, Dexamethasone, Diethyldithiocarbamate, Diltiazem, Dirithyromycin, Disulfiram, Entacapone, Erythromycin, Ethinyl estradiol, Fluconazole, Fluoxetine, Fluvoxamine, Gestodene, Grapefruit juice, Indinavir, Isoniazid, Ketoconazole, Metronidazole, Mibefradil, Miconazole, Nefazodone, Nelfinavir, Nevirapine, Norfloxacin, Norfluoxetine, Omeprazole, Oxiconazole, Paroxetine, Propoxyphene, Quinidine, Quinine, Quinupristine and dalfopristin, Ranitidine, Ritonavir, Saquinavir, Sertindole, Sertraline, Troglitazone, Troleandomycin, Valproic acid.

6.3.2 Pharmacodynamic interactions with PF-04457845: Due to the mechanism of action as selective inhibitor of fatty acid amide hydrolase, pharmacodynamic drug interactions may be hypothesized for the following compounds or situations: metabolic diseases such as abdominal obesity and associated metabolic changes, and diabetes; β -amyloid-linked events; Huntington's disease; sedative use; and other compounds influencing the endocannabinoid system such as cannabinoid receptor ligands (rimonabant); use of Nonsteroidal Anti-inflammatory Drugs. As a result of the above hypothetical pharmacodynamic interactions special care may have to be taken when PF-04457845 is administered to patients with a background of metabolic diseases and use of sedatives and other CNS active compounds such as analgesics / anti-inflammatories. None of these are absolute contraindications. In the absence of pharmacodynamic studies, clinical judgement will need to be exercised to determine the risk:benefit of other drugs taken concomitantly with PF-04457845.

6.4 Contraception: Participants will be provided with information on acceptable methods of contraception as part of the informed consent process, and will be required to use one of the below approved methods of contraception for the duration of the study. Participants will be asked to inform the study staff immediately if either they or their sexual partner has become pregnant while participating in the study. Participants will be asked to document their method of contraception and sign to acknowledge that they will continue to use contraception from signing of consent until two weeks after the last dose of study medication.

6.4.1 Male Participants: From signing of informed consent until 2 weeks after the last dose of study medication, non-sterilized male participants who are sexually active with a female partner of childbearing potential must agree to use barrier contraception (e.g. a condom with or without spermicidal cream or jelly). In addition, they must be advised not to donate sperm during this period.

6.4.2 Female Participants: From signing of informed consent until 2 weeks after the last dose of study medication, female participants of childbearing potential (Women of Child Bearing Potential: WOCBP) who are sexually active with a non-sterilized male partner must use a highly effective method of contraception (from the list below). In addition, they must be advised not to donate ova during this period.

6.4.3 Methods of Contraception: Acceptable contraceptive methods for WOCBP participants include: double barrier contraception or a combination of a barrier contraception and a hormonal implant, injectable, combined oral contraceptive, or a male partner who has had a vasectomy; IUD or tubal ligation.

6.5 **Pregnancy:** If any participant is found to be pregnant during the study, participation in the treatment phase must be immediately terminated. The participant should stop taking the study medication and return any remaining study medication as soon as possible. If possible, the participant should complete the follow up phase which is to collect safety data. Furthermore, the investigator should make every effort to ensure that the participant has established follow up care with a medical provider (OBGYN). The pregnancy should be followed up by the site investigator to determine outcome (including spontaneous or voluntary termination), details of birth, and the presence or absence of any birth defects, congenital abnormalities, or maternal and/or newborn complications.

6.6 Randomization Criteria: Participants who meet all inclusion and exclusion criteria will be randomized at the time of the Week 1 visit in a 1:1 ratio of PF-04457845 to placebo using random block sizes of 2 and 4, stratified by site and degree of cannabis use (CUD at the level of moderate (4-7 [of 11] symptoms) or severe (8-11 [of 11] symptoms)) based on DSM-5 criteria. These variables were chosen because they are the most likely to strongly affect outcomes measures. Random treatment assignment will be done using a centralized randomization process.

6.7 Enrollment:

Participants will be enrolled at each site by competitive enrollment (or at a rate of approximately 8 subjects per month or about 2 subjects per month per site) until up to approximately 260 participants have been enrolled, or until 8 weeks before the drug expiry date (**Figure 14**). The current batch of PF-04457845's expiration date is currently 10/31/2022.

[figure not shown]

Figure 14: Participant Enrollment

6.8 Enrollment by Race and Ethnicity: The sample recruited for this study needs to be composed of as close to70% men and 30% women as possible. Additionally, the sample will be composed of approximately 4% American Indian/Alaska Native, 6% Asian, 30% Black or African American, 50% White, and 9% greater than one race. Please refer to **Table 11** for planned inclusion enrollment broken down by ethnic categories. To ensure that these ethnic and racial divides are met, each site will submit to the Coordinating Center periodic enrollment reports (every 6 months). The Coordinating Center will then instruct each site on which ethnic categories still need to be met.

Table 11: Targeted Enrollment by Ethnic Categories

Racial Categories Not Hispanic or Latino	Hispanic or Latino	Total

APPROVED BY THE YALE UNIVERSITY IRB 5/1/2022

	Female	Male	Unknown	Female	Male	Unknown	
American Indian or Alaska Native	1	6	0	0	0	0	7
Asian	2	13	0	0	0	0	15
Native Hawaiian or Other Pacific Islander	0	0	0	0	0	0	0
Black or African American	24	42	0	2	17	0	85
White	35	80	0	3	11	0	129
More than One Race	6	6	0	5	7	0	24
Unknown	0	0	0	0	0	0	0
Total	68	147	0	10	35	0	260

6.9 Screen Failures: Screen failures are defined as participants who consent to participate in the clinical trial but are not subsequently randomized to the study intervention or entered in the study. A minimal set of screen failure information is required to ensure transparent reporting of screen failure participants, to meet the Consolidated Standards of Reporting Trials (CONSORT) publishing requirements and to respond to queries from regulatory authorities. If the participant is found to be ineligible at Screening, the investigator should complete the source document. Minimal information includes demographics, screen failure details, eligibility criteria, and any serious adverse events (SAE). Subject ID numbers assigned to participants who fail screening should not be reused.

The primary reason for screen failure should be recorded in the source document using one of the following categories:

- Adverse Event.
- Did not meet inclusion criteria or did meet exclusion criteria (specify reason).
- Important protocol deviation.
- Lost to follow-up.
- Voluntary withdrawal (specify reason).
- Other (specify reason).

Individuals who do not meet the criteria for participation in this trial (screen failure) may be rescreened if the reason that they were excluded is no longer an issue (e.g., an underage participant who now falls within the permitted age range, or a participant who has stopped taking a prohibited medication). However, participants who were initially screen failures cannot be rescreened for this study more than twice. Rescreened participants should be assigned the same participant number as for the initial screening.

